5. ANALYSIS POPULATIONS

The Safety Population will consist of all subjects who underwent the planned surgery and received study treatment. All analyses based on the safety population will be by actual treatment received.

The PK Population will consist of subjects who received study drug and provided at least one quantifiable plasma concentration. All analyses will be by actual treatment received.

All analyses of data collected for exploratory purposes (i.e., data related to pain intensity scores and opioid consumption) will be conducted using the safety population, and analyzed according to the actual treatment received.

6. STATISTICAL METHODS OF ANALYSIS

6.1 General Principles

The statistical analyses will be reported using summary tables, listings, and figures (TLFs). All analyses and tabulations will be performed using SAS[®] Version 9.4 or later, with the exception that pharmacokinetics descriptive statistics will be performed using Sigmastat and Microsoft Excel. Continuous variables will be summarized using descriptive statistics [sample size (n), mean, standard deviation (SD), minimum, median, and maximum]. Categorical variables will be tabulated with number and percentage of subjects. Unless otherwise noted, percentages will be based on the number of subjects in the treatment group or group within the analysis population.

Individual subject data will be provided in listings. All listings will be sorted by group, treatment (Group 1), surgery type (Group 2), site, subject and, if applicable, collection date and time.

Unless otherwise stated, summaries will present data pooled from all sites.

Unless otherwise noted, tabulations of categorical data will present only those categories appearing in the data.

For tables presenting summaries of pain intensity scores, if more than one score is presented for a specific timeframe/timepoint of interest, the highest score within that specific timeframe/timepoint should be used.

Unless otherwise stated, separate summaries and data listings will be presented for each age group (Group 1, Group 2). Unless otherwise noted, summaries for Group 1 will be presented by treatment group and summaries for Group 2 will be presented by type of surgery (Spine or Cardiac).

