Part 1, Group 2, is a single-arm (EXPAREL 4 mg/kg), open-labeled, PK evaluation study in subjects aged 6 to less than 12 years undergoing spine or cardiac surgery. The sample size is a total of 15 subjects. Subjects will receive a single dose of EXPAREL 4 mg/kg (maximum 266 mg) intraoperatively at the end of surgery via local infiltration.

The total sample size for Part 1 is 45 subjects aged 6 to less than 17 years, with 30 subjects in Group 1 and 15 subjects in Group 2.

Part 2 (Safety) - Subjects aged 6 to less than 17 years

Part 2 is a multicenter, randomized, open-label, safety study in 45 subjects aged 6 to less than 17 years undergoing spine or cardiac surgeries. There will be two treatment groups: Group 1 will include subjects aged 12 to less than 17 years, while Group 2 will include subjects aged 6 to less than 12 years.

Part 2, Group 1, is an active-controlled, open-labeled, safety evaluation study in subjects aged 12 to less than 17 years undergoing spine surgery. The active comparator will be bupivacaine HCl. The sample size is a total of 30 subjects (15 subjects per treatment group). Subjects will be randomized 1:1 to receive either a single dose of EXPAREL 4 mg/kg (maximum 266 mg) or bupivacaine HCl 2 mg/kg (not exceeding a maximum bupivacaine HCl dose of 175 mg total) intraoperatively at the end of surgery via local infiltration.

Part 2, Group 2, is a single-arm (EXPAREL 4 mg/kg), open-labeled study in subjects aged 6 to less than 12 years undergoing spine or cardiac surgery. The sample size is a total of 15 subjects. Subjects will receive a single dose of EXPAREL 4 mg/kg (maximum 266 mg) intraoperatively at the end of surgery via local infiltration.

The total sample size for Part 2 is 45 subjects aged 6 to less than 17 years, with 30 subjects in Group 1 and 15 subjects in Group 2.

The overall safety assessments will include all 45 subjects from Part 1 and all 45 subjects from Part 2, with a total of 90 subjects.

Subjects will be screened within 30 days prior to study drug administration. During the screening visit, subjects will be assessed for past or present neurologic, cardiac, and general

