12.3. Safety Assessments

The following safety measurements will be conducted at the time points specified:

• Vital signs (temperature, resting heart rate, respiratory rate, oxygen saturation, and blood pressure) at screening; upon arrival in the post-anesthesia care unit (PACU); at 2, 4, 8, 12, 24, 36, 48, 60, 72, and 96 hours after the end of study drug administration; at hospital discharge; and on Day 30.

- Neurological assessment at screening; at 2, 4, 8, 12, 24, 36, 48, 60, 72, and 96 hours after the end of study drug administration; at hospital discharge; and on Day 30 (Part 1 only, Appendix 3).
- Clinical laboratory tests (hematology, chemistry, and urinalysis) at screening; at baseline (on Day 1 prior to surgery) and at 96 hours after the end of study drug administration (see Appendix 4).
- AEs from the time the ICF is signed/assent is obtained till Day 30.

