13.1.2. Neurological Examination

A neurological assessment will be conducted during Part 1 only at the following time points: at screening; at 2, 4, 8, 12, 24, 36, 48, 60, 72, and 96 hours after the end of study drug administration; at hospital discharge; and on Day 30. The examination will include the subject's orientation. Additionally, subjects aged 6 years or older will be asked whether he or she is experiencing any numbress of the lips, the tongue, or around the mouth; hearing problems; or muscle twitching (see Appendix 3). If the subject answers "yes" to any of these questions, the event should be recorded as an AE and additional safety procedures should be conducted as appropriate (see Section 13.1.7).

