13.2. Screening Procedures

- Explain study purpose and procedures.
- Obtain written informed consent/assent before performing any study-related procedures.
- Assess eligibility.
- Record relevant medical/surgical history, demographics, and baseline characteristics.
- Conduct urine pregnancy test for females of childbearing potential (Part 1 only).
- Perform physical examination.
- Perform neurological assessment (see Appendix 3; Part 1 only).
- Conduct clinical laboratory tests (hematology, chemistry, and urinalysis) (see Appendix 4).
- Conduct a urine drug screen and alcohol breath test at the investigator's discretion. Subjects with a positive result will be excluded from the study.
- Measure vital signs (temperature, resting heart rate, respiratory rate, oxygen saturation, and blood pressure) after subject has rested in a supine position.
- Conduct 12-lead ECG after subject has rested in a supine position.
- Record a pain intensity score using one of the following instruments:
 - 0 11-point NRS-R for subjects aged 12 to less than 17 years (Appendix 1)
 - CAS for subjects aged 6 to less than 12 years (Appendix 2)
- Record concomitant medications.
- Record AEs starting at the signing of the ICF/assent.

All subjects who are screened for enrollment, but do not meet eligibility criteria, who decline to participate, or whose parent or guardian decline the subject's participation, will be documented on a screening log with the reason for non-participation.

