15.6. Statistical Analyses

Continuously valued data will be summarized using descriptive statistics (n [number of subjects contributing data], mean, SD, median, minimum, and maximum). Discretely valued data will be tabulated (n and percentage) by category. The denominator for all percentages will be the number of subjects who underwent the planned surgery.

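### The neurological tables name no Part and no assessed-subject denominator; if only Part 1 is assessed and the Parts are pooled, Group 1 percentages print at half the assessed rate

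*SAP*

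**What the plan says.** **Denominator.** SAP 6.1 gives the default: "Unless otherwise noted, percentages will be based on the number of subjects in the treatment group or group within the analysis population". Protocol 15.6 points the same way: "The denominator for all percentages will be the number of subjects who underwent the planned surgery". Neither rule refers to subjects actually assessed.

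**Population.** SAP section 5 sets no Part limit: "The Safety Population will consist of all subjects who underwent the planned surgery and received study treatment". Protocol 9.1 counts both Parts towards safety: "The overall safety assessments will include all 45 subjects from Part 1 and all 45 subjects from Part 2".

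**Who is assessed.** Protocol 13.1.2 is explicit: "A neurological assessment will be conducted during Part 1 only at the following time points". The time points it then lists run from screening through 96 hours, discharge and Day 30. Protocol 12.3 carries the same tag ("at hospital discharge; and on Day 30 (Part 1 only, Appendix 3"), as do the screening list in 13.2 ("Perform neurological assessment (see Appendix 3; Part 1 only") and the lists in 13.6 and 13.8. Protocol 9.1, 13.5, Table 1, Appendix 3 and the SAP overview (section 3) mention the assessment with no Part limit.

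**Tables.** SAP 6.8.3 asks for numbers and percentages by treatment in Group 1 and by surgery type in Group 2. Tables 14.3-2.1.1 to 14.3-2.1.3 are titled for the Safety Population and name no Part. Neither place gives its own denominator.

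**The concern.** The proportion of subjects oriented and the proportion with any neurologic event are named safety endpoints (Protocol 12.4). The study tests no hypothesis, so these endpoints are read directly from the descriptive tables.

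If Part 2 subjects are never assessed but are counted in the column N, they act in the percentage as though they had been assessed and had no finding. An absolute event rate then looks lower than it was among the children examined. Two programmers following this SAP, one pooling the Parts and one paging by Part, could print rates that differ twofold from the same data.

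**Working it through.** **1. Planned numbers.** Each Part has 15 EXPAREL and 15 bupivacaine HCl subjects in Group 1, and 15 EXPAREL subjects in Group 2 (Protocol 9.1). EXPAREL: 15 × 4 = 60. Bupivacaine HCl: 15 × 2 = 30. Total 90. This reproduces the protocol synopsis (60, 30 and 90).

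**2. Is the assessment Part 1 only?**

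| Favours Part 1 only | Leaves it open |
|---|---|
| Protocol 13.1.2, explicit for every time point | Protocol 13.5 and Appendix 3, untagged |
| Tags in Protocol 12.3, 13.2, 13.6, 13.8 | Table 1 tags two other rows (pregnancy test, drug and alcohol screen) as Part 1 only, but not this row |
| PK sampling is also untagged in 13.5 and Table 1, yet is Part 1 only under Protocol 9.1, so silence there is weak evidence | Protocol 9.1 and SAP section 3 list the assessment to 96 hours with no Part limit |
| Neurological rows are excluded from the pooled Group 1 baseline Table 14.1-3.2.1 | The pooled Group 2 baseline Table 14.1-3.2.2 carries no such exclusion |

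The explicit text favours Part 1 only, but the documents need reconciling.

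**3. Do the tables pool the Parts?** Three things favour pooling: the Safety Population has no Part limit; the table titles name no Part; and SAP 6.1 separates output by age group only ("Unless otherwise stated, separate summaries and data listings will be presented for each age group (Group 1, Group 2"), whereas SAP 6.9.2.1 does ask for results by Part. Against it, SAP section 10 requires a page break between Parts. The neurological shell also lacks the programmer note, used on some other shells, that both Parts are combined. That absence proves little, because the vital-sign and AE shells lack the note too. Pooling is therefore the likelier reading, but it is an inference.

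**4. Size if both conditions hold.** Let n1 be the assessed (Part 1) subjects in an arm, n2 the unassessed (Part 2) subjects, and k the subjects with a finding.

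Printed rate ÷ assessed rate = [k/(n1 + n2)] ÷ [k/n1] = n1/(n1 + n2) = 15/(15 + 15) = 0.50.

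| k | Assessed rate, k/15 | Printed rate, k/30 |
|---|---|---|
| 1 | 6.7% | 3.3% |
| 2 | 13.3% | 6.7% |
| 3 | 20.0% | 10.0% |
| 15 (all oriented) | 100% | 50% |

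Both arms are halved, so their ratio is unchanged, while absolute rates and differences are halved. If treated numbers per arm and Part ranged from 13 to 17 (an assumption), the factor would run from 13/30 = 0.43 to 17/30 = 0.57.

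**5. If either condition fails.** With paging by Part, the Part 1 page has N = 15 and the factor is 15/15 = 1.00. If Part 2 is also assessed, there is no dilution beyond missed visits.

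**6. Group 2 and the both-groups spine table.** The factor depends on the spine/cardiac split in each Part, which the documents do not give. No figure is claimed.

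**7. Recovery.** The shell prints counts for each answer. With 3 Yes and 12 No, the assessed number is 3 + 12 = 15, and 3/15 = 20% can be worked out even when 10% is printed.

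**The case against.** The halving needs two conditions, and the documents prove neither. Table 1 knows how to mark a row as Part 1 only and does not mark this one. The page-break rule may mean that the tables were always to be paged by Part. This stands, and it is why the figure can only be conditional.

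The practical harm is also limited. Counts let a reader recover the assessed rate, and a missing-data row under SAP section 10 would expose the gap, though it would not correct the Yes and No percentages. Findings at the assessment must also be recorded as AEs, so they reach the TEAE tables. The baseline and by-time-point tables could show 100% and 50% oriented at screening for the same children, but they are labelled with different populations (PK and Safety). All of this stands.

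A further objection is that a per-time-point denominator departs from Protocol 15.6 and could hide Part 1 children who missed a visit, whose absence may be informative. That is fair. It is met by printing the assessed n beside the arm N.

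A reader might go further and infer that the plan will understate neurological toxicity by half, or that it biases the comparison of EXPAREL with bupivacaine HCl. The documents do not support either reading. The first treats two open questions as settled and overlooks the printed counts and the AE route; the second fails because both arms are affected alike in ratio. Nor does the exclusion in the pooled Group 1 baseline table prove Part 1 only, since the Group 2 counterpart lacks it.

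**Conclusion.** The point holds as a conditional presentation fault of minor severity. What is established is that the protocol is inconsistent about which Parts undergo the neurological assessment, and that the SAP's neurological tables state neither their Part scope nor a denominator suited to it. Under the default rule, if the assessment is Part 1 only and the tables pool the Parts, Group 1 percentages print at 0.50 of the assessed rate. This assumes that the planned 15 subjects per arm are treated in each Part and that all 15 in Part 1 are assessed. If either condition fails, this dilution disappears.

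**What to change.** - **Protocol:** state which Parts are assessed, reconciling 12.3, 13.1.2, 13.2, 13.6 and 13.8 with 9.1, 13.5, Table 1 and Appendix 3. Align the SAP overview and the Group 2 baseline shell with the answer.
- **SAP 6.8.3 and Tables 14.3-2.1.1 to 14.3-2.1.3:** state whether the Parts are pooled. Base percentages on subjects assessed at each time point. For the tabulation at any time after baseline, use subjects with at least one post-baseline assessment. Print that n beside the arm N so that missed visits stay visible. Label the tables Part 1 if that is the scope.
- **SAP 6.11:** record the exception to SAP 6.1 and Protocol 15.6.

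The denominator rule works under either scope and discards no data. The cost is one protocol clarification, a sentence or two in SAP 6.8.3, a line in 6.11, and minor programming for three tables. The downside is a smaller displayed n.

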6.1.1 Handling Missing Values

6.1.1.1 Exposure, Surgery, and Rescue Opioid Medication Date or Time

It is expected that all necessary information on study drug exposure, surgery, and postsurgical rescue medication (dates and times) will be complete. Any such information that is missing and cannot be obtained through query resolution may be imputed, on a case-by-case basis, in a conservative manner that minimizes bias. For example, if opioid rescue pain medication taken on Day 1 has no time of administration recorded, the imputed time will be the end of surgery.

6.1.1.2 Postsurgical Opioid Medication

Opioid rescue pain medication usage will be summarized based on oral morphine equivalent dosage (MED mg).

If a subject is discontinues the study early (e.g., dies, withdraws consent, is withdrawn from the study, or is lost to follow-up) before the end of the analyses time interval (e.g., 72 hours after end of surgery), his or her total opioid rescue pain medication usage through the time interval will be a projected amount.

For the calculation of the total amount of opioid medication used from the end of surgery through, for example, 72 hours, if a subject is discharged at x < 36 hours after end of surgery, the total postsurgical opioid consumption through 72 hours will be calculated as $72 * \frac{D_{0,x}}{x}$, where $D_{0,x}$ is the opioid consumption during the initial *x* hours (inclusive) postsurgery. If a subject is discharged at $36 \le x < 72$ hours, the total postsurgical opioid consumption through 72 hours will be calculated as $D_{0,x} + D_{2x-72,x}$, where $D_{2x-72,x}$ is the opioid consumption from 2x-72 hours (exclusive) through *x* hours (inclusive). For example, if a subject is discharged at x=70 hours, the postsurgical 0 to 72 hours opioid consumption will be calculated as the consumption during the first 70 hours plus the consumption between 70 and 72 hours, which is imputed by the consumption between 68 and 70 hours.

If an opioid medication is taken on the discharge day, but the time of dosing is missing, it will be imputed as time of discharge or 12:00 pm on the discharge day, whichever is later. If opioid is taken after day of discharge, and the time of dosing is missing, it will be imputed as12:00 pm.

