11.6.3. After Surgery

Permitted

- Postsurgical pain management will consist of institution's standard of care in case of insufficient analgesia.
- Parenteral antiemetic medication may be administered, as needed.

Restricted

• Avoid additional use of local anesthetics within 96 hours following administration of EXPAREL.

All postsurgical analgesics administered must be documented till 96 hours after surgery.

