Treatment-emergent adverse events (TEAEs) are those with onset on or after the start time of study drug administration, and before or at the end of the study (expected to be Study Day 30 ± 3 days).

Time 0 (zero)

Time 0 is defined as the time of the end of study drug administration, with the exception of AE's and concomitant medications. Time 0 for AE's and concomitant medications are defined as the time of the start of study drug administration.

Time Deviation

For PK sampling time window, *Time Deviation* is the difference (actual – start/end of target window of assessment) between the actual and target window of assessment in the PK sampling. If sampling occurred before the beginning of target window of assessment, time deviation will be calculated by subtracting the actual time from the beginning of the target window of assessment. If the sampling occurred after the end of target window of assessment, time deviation will be calculated by subtracting the actual sampling time from the end of the target window of assessment. Any samples occurring with the target window will have a time deviation of 0.

Baseline

Baseline measurement or assessment is defined as the last available measurement or assessment prior to the start of study drug administration.

Last Follow-up Time

For subjects who withdraw prematurely, the last follow-up time will be defined as the maximum of the last pain or any other study assessment, the last concomitant medication start or end datetime, and the last adverse event start or end datetime.

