6.9.2 Opioid Consumption

Opioid medications will be converted to oral morphine equivalent dose (MED mg) using the appropriate conversion factor from Table 8 for all summaries. Opioids are collected on the Post Surgical Pain Medication and Prior/Concomitant Medications eCRF pages. The amount of total opioid dose will be calculated as the sum of the oral morphine equivalent of all opioids taken after surgery up to the timepoint of interest. Subjects with no opioid use during the period in question will be assigned a dose of 0 for summaries and changed to the lesser of 0.1 or half of the smallest total amount observed in the study, whichever is smaller, prior to being transformed with the natural logarithm for analysis. Total postsurgical opioid dose will be calculated through 24, 48, and 72 hours. In addition to the descriptive statistics for continuous data, geometric mean (GM) and coefficient of variation (CV) will also be included and mean and SD will be excluded.

For the calculation of the total dose through 72 hours, if a subject's last follow-up time is 72-x hours, then the approach described in Section 6.1.1.2 is used.

Medication	Unit	Route	Oral Morphine Conversion Multiplication Factor
Morphine, Morphine Sulfate	mg	IV,IM,SC	3
Morphine	mg	РО	1
Morphine	mg	R	1
Buprenorphine	mcg	IM	75
Buprenorphine	mcg	SL	37.5
Codeine (Tylenol 3, acetaminophen-coedine,	mg	РО	0.15
Paracetamol Forte, Tylenol 4,)			
Codeine Phosphate	mg	IM	0.24
Demerol, Meperidine, Pethidine	mg	IV,SC	0.3
Demerol, Meperidine, Pethidine	mg	РО	0.1
Fentanyl, Remifentanil	mcg	IV,PO,IM,TD	300
Hydromorphone	mg	R	4
Hydromorphone (Dilaudid)	mg	IV,IM,SC	20
Hydromorphone (Dilaudid)	mg	РО	4
Hydromorphone (Dilaudid)	mg	EP	45
Ketobemidone, Oxycodone	mg	IV	3
Methadone	mg	IM	3
Methadone	mg	РО	1.5
Methadone	mg	IV	6
Nalbuphine/Nallouphine (Nubain/Manfine)	mg	IV,IM,SC	3
Oxycodone, Oxycocet, Percocet, acetaminophen-	mg	PO	1.5
oxycodone, Oxycodone HCl			
Oxymorphone	mg	РО	3
Oxymorphone	mg	IM,SC	30
Pentazocine/Acetaminophen	mg	РО	0.2
Pentazocine/Naloxone	mg	PO	0.2

Table 8 Oral Morphine Equivalents

Pentazocine	mg	IM	1
Tapentadol	mg	PO	0.3
Ultram, Tramadol, Tramacol hydrochloride	mg	PO,IM	0.25
Vicodin, Norco, Lorcet, Lortab, hydrocodone-	mg	PO	1
acetaminophen, Ketobemidone			

Key: EP = Epidural; IM = Intramuscular; IV = Intravenous; INS = Intra Nasal Spray; NA = Not Applicable; PO = Oral; R = Rectal; SC = Subcutaneous; SL = Sublingual; TBD = To Be Determined; TD = Transdermal

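### SAP 6.1.1.2 and 6.9.2 give three inconsistent triggers for projecting opioid totals; the formulas as written would replace opioid use recorded after hospital discharge

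*SAP*

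**What the plan says.** **Trigger 1, study discontinuation.** SAP 6.1.1.2 opens with "If a subject is discontinues the study early (e.g., dies, withdraws consent, is withdrawn from the study, or is lost to follow-up" and says that such a subject's total over the interval will be a projected amount.

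**Trigger 2, discharge.** The next paragraph supplies the calculation under a different condition: "if a subject is discharged at x < 36 hours after end of surgery", the 72-hour total is 72 × D(0,x)/x, where D(a,b) is the opioid amount between hours a and b. For discharge at 36 ≤ x < 72 it is D(0,x) + D(2x−72, x). The example reads "if a subject is discharged at x=70 hours, the postsurgical 0 to 72 hours opioid consumption will be calculated" from the first 70 hours plus the last two hours, "which is imputed by the consumption between 68 and 70 hours". The paragraph after that sets clock times for doses on the discharge day, and also for later ones: "If opioid is taken after day of discharge, and the time of dosing is missing".

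**Trigger 3, last follow-up.** SAP 6.9.2 says "if a subject's last follow-up time is 72-x hours, then the approach described in Section 6.1.1.2 is used". SAP Section 4 defines the term: "For subjects who withdraw prematurely, the last follow-up time will be defined as the maximum of the last pain or any other study assessment", or the last concomitant-medication or adverse-event time. Section 6.9.2 also takes opioids from two eCRF pages (post-surgical pain medication, and prior/concomitant medications) and reports totals through 24, 48 and 72 hours.

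**Recording period.** Protocol 9.1 sets no minimum stay and provides home nurse visits to 96 hours. Protocol 11.6.3 states "All postsurgical analgesics administered must be documented till 96 hours after surgery"; the Synopsis (Other Assessments) and Table 1 footnote 6 also give 96 hours. The pain-management paragraphs of the Synopsis, Protocol 9.1 and SAP Section 3, and Protocol 12.5, stop at hospital discharge. Protocol 11.1 refers to hospitalization only.

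**The concern.** The three triggers select different children. A child who goes home at 30 hours and completes every later assessment is not projected under the first or third trigger, but is projected under the second. The second is the one attached to the formulas, so it is the one a programmer would code.

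In that paragraph, discharge most naturally means leaving hospital, because the text that follows speaks of the day of discharge and of doses taken after it. That text also shows that the SAP expects opioid records after discharge. The formula would leave them out of the total and substitute the earlier rate of use.

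If use falls over the days after surgery, totals are overstated for children who go home early. If discharge times differ between the two Group 1 arms, or between surgery types in Group 2, the displayed totals differ partly because of the rule. Separately, the symbol x means opposite things in the two sections that have to be used together.

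**Working it through.** **1. Reproduce the SAP's own example.** At x = 70, 2x − 72 = 68, so the window is 68 to 70 hours, as stated. At x = 36 both branches give 2 × D(0,36), so the rule is continuous. At a constant 5 mg/h the true total is 72 × 5 = 360 mg, and the rule returns it:
- x = 24: 72 × 120/24 = 360
- x = 48: 240 + 120 = 360
- x = 70: 350 + 10 = 360

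The formulas are therefore sound when x is elapsed time and nothing is known after x.

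**2. Set the triggers side by side.**

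| Place | Trigger | Meaning of x | Child discharged early, still followed |
|---|---|---|---|
| 6.1.1.2, lead sentence | study discontinuation | none given | not projected |
| 6.1.1.2, formulas and example | discharge | hours elapsed | projected |
| 6.9.2 with Section 4 | last follow-up at 72−x | hours missing | not projected |

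**3. Size if the formula paragraph is followed.** The documents give no opioid time course and no discharge times. As an assumption, let use decline exponentially with half-life h, so that D(a,b) is proportional to 2^(−a/h) − 2^(−b/h). The ratio is the projected total divided by the true D(0,72).

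For h = 24: D(0,24) = 0.5, D(0,48) = 0.75, D(24,48) = 0.25 and D(0,72) = 0.875.
- Discharge at 24 h: 72 × 0.5/24 = 1.5, and 1.5/0.875 = 1.71.
- Discharge at 48 h: 0.75 + 0.25 = 1.0, and 1.0/0.875 = 1.14.

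| Discharge | h = 16 | h = 24 | h = 36 |
|---|---|---|---|
| 24 h | 2.03 | 1.71 | 1.48 |
| 48 h | 1.15 | 1.14 | 1.12 |

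A stepped profile, also assumed, gives the same picture. With 60, 30 and 10 mg recorded in successive 24-hour periods, the recorded total is 100 mg. The projection gives 72 × 60/24 = 180 mg for discharge at 24 h, and 90 + 30 = 120 mg at 48 h. A child with 60 mg by 24 h and a recorded zero afterwards would be reported as 180 mg instead of 60 mg.

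The 24 and 48-hour totals are open to the same problem when discharge precedes those times, because 6.1.1.2 offers 72 hours only as an example.

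**4. The two meanings of x.** They sum to 72 and agree only at 36. Last follow-up at 70 h is x = 70 in 6.1.1.2 but x = 2 in 6.9.2. Entering 2 into the 6.1.1.2 formula would give 72 × D(0,2)/2 = 36 × D(0,2), where D(0,70) + D(68,70) is intended.

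**The case against.** The lead sentence is the only one that says a total will be projected, and it is confined to study discontinuation. The formula paragraph can be read as its arithmetic. Section 6.9.2, which defines the endpoint, calls the rule by last follow-up, a term that Section 4 ties to premature withdrawal. The SAP also speaks elsewhere (the note for the concomitant-medication tables) of discharge from the study. On that reading no recorded use is lost. This stands as far as it goes: overwriting is not the settled plan. It does not settle the matter, since the formulas and example both say discharged and the neighbouring text points to the hospital.

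A reader might infer that post-discharge use is certainly on file for every child, so that restoring it would be enough. The documents do not support this, because several sections stop recording at discharge. Capture through the concomitant-medication page is likely but not uniform across the text. If recorded use were simply substituted, a site that stopped at discharge would have its unrecorded home use counted as zero, and overstatement would become understatement.

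A reader might also take the clash in x as a planned error. With last follow-up at 60 h and x taken as 12, the ratio would be 1.65 to 2.54 over the half-lives above. That would be a programming mistake contradicted by the SAP's worked example, so it is not counted in the size of this point.

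Finally, the opioid endpoints are exploratory, the totals carry no test, Group 2 has no comparator, and individual doses remain in Listings 16.2-7.2.1.1 and 16.2-7.2.1.2. All of this is correct and limits the consequence.

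**Conclusion.** The point holds as an inconsistency in the rule: three triggers, and one symbol with two meanings. Replacement of recorded opioid use follows only if the formula paragraph is applied as written over the lead sentence and the last follow-up condition.

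In that case the 72-hour total is about 1.5 to 2.0 times the true value for discharge at 24 hours and 1.12 to 1.15 times for discharge at 48 hours. These figures assume exponential decline with a half-life of 16 to 36 hours and full recording after discharge. Constant use gives no bias. Any distortion between arms also needs discharge times to differ by arm, on which the documents are silent.

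Only the exploratory opioid totals at 24, 48 and 72 hours are touched; the PK and safety results are not. It should still be corrected, because the remedy is cheap and the choice would otherwise fall to whoever programs the table.

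**What to change.** - **SAP 6.1.1.2:** define x once, as hours from end of surgery to last follow-up, or to the end of opioid recording where that came earlier. Use it in both formulas and the example in place of discharge. Project only when x falls short of the interval being summarised, and give the rule for 24 and 48 hours as well as 72.
- **Discharged subjects still in follow-up:** state that their totals use the opioids recorded on both eCRF pages, with no projection.
- **SAP 6.9.2:** change the condition to last follow-up time being x < 72 hours, so that x has the same meaning as in 6.1.1.2.
- **Recording period:** reconcile the 96-hour statements (Protocol Synopsis, Other Assessments; Table 1 footnote 6; 11.6.3) with those that stop at discharge or hospitalization (Protocol Synopsis, pain-management paragraph; 9.1; 11.1; 12.5; SAP Section 3). Say how a child whose opioid recording ended at discharge is handled, so that missing home use is not entered as zero.

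The cost is wording in the SAP and a clarification of the Protocol. No new data are needed where opioids were recorded to 96 hours. Where a site stopped at discharge, the end of recording has to be identified for each child.
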